A dose escalation study was performed in 8 healthy subjects in a non-randomized, open-label pharmacokinetics (PK) study with 250 mg NR orally administered on days 1 and 2, then uptitrated to peak dose of 1000 mg twice daily on days 7 and 8. No clinically significant changes were seen at NR dose up to 1000 mg orally twice daily in any of the five pre-specified safety endpoints, i.e., potassium, creatine phosphokinase (CPK), glucose, uric acid and alanine aminotransferase. Serum potassium decreased by an average of 0.4 mEq/L, which was statistically significant (p = 0.015) but the individual levels remain in normal range. There was a slight though statistically significant decrease for hematocrit (mean difference = -2%, p = 0.005), hemoglobin (-0.4 g/dL, p = 0.04), and platelet count (-20,000/µL, p = 0.03). There were no significant changes in blood pressure, body temperature, body weight, white blood cell count, lactate dehydrogenase or aspartate aminotransferase. In addition, there were no significant changes in serum levels of sodium, chloride, urea nitrogen, creatinine, or in white blood cell differential [38].

In an investigator-initiated randomized, placebo-controlled, double-blinded study of 40 healthy men with BMI> 30 kg/m² NR was administered at a dose of 1000mg twice daily for 12 weeks [39]. Adverse events (AEs) were reported in 4 subjects in the NR group which included pruritis, excessive sweating, bloating and transient changes in stool. There were two AEs in the placebo group which were acid reflux and loose stools. The severity was mild in all cases. Laboratory analysis for blood counts and chemistries at 6 weeks revealed no abnormalities in the NR group.

A recent report evaluated a combination of NR with an anti-oxidant pterostilbene (PT; NRPT) in 24 hospitalized patients with AKI with a single dose ranging from 250mg NR, 500mg NR, 750mg NR to 1000mg NR twice a day [15]. Compared to the baseline timepoint, NRPT dose 500 mg/100 mg twice a day increased whole blood NAD+ levels 47% at 48 h, (p = 0.04). Whole blood NAD+ levels in patients with AKI receiving placebo decreased by 50% at 48 h (p = 0.05). Compared to placebo, there was no significant difference in creatinine, estimated glomerular filtration rate (eGFR), electrolytes (sodium, potassium), liver enzymes (ALT, AST, ALP), hemoglobin, white blood count or platelet count in patients treated with NRPT at 48 h. NRPT

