N-methyl-2-pyridone-5-carboxamide or 2PY, a major metabolite of NAM, is considered a uremic toxic in patients with impaired renal function [50, 51]. While serum 2PY level may increase significantly with NAM supplementation [46], the intracellular concentration may not rise compared to baseline in hemodialysis patients [52]. In general, available data conclude that NAM is safe and tolerable in adults at doses of below 3 g/day [53]. Taken together the available safety data of niacin and NAM indicate that in patients with impaired renal function both agents are tolerable [54-56]. The prominent side effects of NAM at therapeutic doses (i.e., 1000 mg/day) are gastrointestinal symptoms (mainly diarrhea) that generally resolve on treatment withdrawal or discontinuation. Develeopement of hetatoxicity require massive dose of NAM – 9 g/day and prolong therapy for months may cause thromobocytopenia [55, 56]. Based on the available data, the known potential risks of NR can be divided into those that are likely and those that are rare.

Likely

These risks are expected to occur in 5-15 participants or less out of 100 participants.

- Gastrointestinal disorders: nausea, heart burn (e.g., indigestion, gas, upper abdominal discomfort, and bloating), diarrhea, transient changes in stool;
- Musculoskeletal disorders: back soreness, muscle soreness;
- Skin disorders: pruritus, flushing, hives;
- Other disorders: leg cramps, increased bruising, excessive sweating;
- Laboratory findings: liver function abnormalities; decrease in blood urea nitrogen;

Rare

The following risk may occur at an unknown rate:

- Hematologic profile e.g., <10% reduction in hemoglobin and platelet counts
- Allergic reaction or hypersensitivity

There is no available data on potential interactions between NR and standard treatment for comorbidities (concurrent medications) or any investigational agents for the treatment of COVID-19. Administering NR concurrently with other agents may lead to antagonism or synergy or may have no effect.

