8.2 SAFETY AND OTHER ASSESSMENTS

Assuring participant safety is an essential component of this protocol. NR is considered GRAS (Generally Recognized as Safe) as filed for designation to FDA. Use of NR for the prevention and or treatment of AKI in COVID-19 positive participants, however, raises unique safety considerations. This protocol addresses these considerations through:

- Exclusion criteria designed to prevent potential overdose effects by excluding participants with concomitant intakes of niacin, nicotinamide, and NR;
- Daily assessment of participants health status;
- Systematic collection of safety outcomes;
- Structured reporting of adverse events;
- Appointment of independent safety adjudication committee (SAC)

Study procedures and evaluations to be done as part of the study to monitor safety and support the understanding of the study intervention's safety. For all visits starting from baseline until the last follow-up visits, the following assessments will be completed:

- Physical examination: A physical examination at the baseline visit or a record of routine physical examination performed within 24 hours prior to consenting, and at Day 30, and Day 90 follow-up visits.
- During the 10-day intervention period, participant's health status will be obtained on a daily basis from the participant and from EHR. Health status of participants will be collected by the study team at Day 30, and Day 90 follow-up visits. Participants will be specifically asked for any new symptoms on a daily basis.
- The safety clinical laboratory parameters will be performed at each visit while hospitalized. Any laboratory tests performed as part of routine clinical care (Clinical Laboratory Tests) within the specified visit window will be used for safety laboratory testing (see Table 4).

Research laboratory tests:

Blood for the first whole blood NAD+ level will be drawn within 6 hours prior to the first study drug dosing (i.e., baseline NAD+ level, Day 1). Whole blood NAD+ level will be measured daily for a total of 10 days while hospitalized starting at the baseline.

Safety laboratory from routine daily laboratory tests:

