Safety laboratory will be performed at Visit 1 and then every visit thereafter for hospitalized participants. Clinical laboratory tests performed as part of routine clinical care in the 24 hours prior to first study drug dose will be accepted for the baseline (Day 1) safety laboratory tests. Any clinical laboratory tests (see Table 4) performed as part of routine clinical care within the specified visit can be used for safety laboratory testing within the period of hospitalization up to 10 days prior to starting the study drug.

Rationale for specific safety laboratory tests:

Several case studies reported that COVID-19 patients may present with mild symptoms such as muscle weakness with elevated CPK and laboratory confirmation of rhabdomyolysis [75-77]. Although, the incidence of rhabdomyolysis in COVID-19 is not known, several case reports indicate an association between rhabdomyolysis and AKI in COVID-19 patients [78-80]. One study reported elevated levels of CPK in about 14% of patients [21], suggesting involvement of muscle injury.

NR has been evaluated on the development of aging-induced non-alcoholic fatty liver disease in mice [81]. It was found that AST (aspartate transaminase) level was significantly reduced by NR supplementation while the alanine transaminase (ALT) level decreased without significance compared to baseline [81]. One human study demonstrated that NR significantly reduced AST level at day 56 from baseline [8]. It is likely that COVID-19 patients will be receiving different medications for comorbidities and as per the FDA guidance [82], liver function tests will be performed as listed in the Table 4.

Research laboratory tests	Safety laboratory tests	Repository			
Daily during Study Day 1 to Study Day 10					
Blood (daily):	Blood:	Blood:			
1.Whole blood NAD+	1. CPK on day 5	 Future biomarkers 			
2. Serum creatinine	2. Liver function tests on day 5	 Genetic analysis 			
(performed if	3 . Daily CBC and platelets				
routine test is	(performed if routine test is	Urine:			
missed or not	missed or not available)	 Future biomarkers 			
available)					
		Note: additional collections at			
Urine (daily):		hour 3 and hour 6 post-			
1. Urinalysis		randomization study drug for			
2. Urine creatinine		PK analysis			
3. UACR and UPCR					
4. Urine glucose					
5. Lactate					
6. Urine phosphate					
7. Urine NAD+					
metabolome					
Day 30 and Day 90	E				
Blood:		Blood:			
1. Serum creatinine		• Future biomarkers			

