8.3.6 SERIOUS ADVERSE EVENT REPORTING

The study investigators will report all unexpected serious adverse events and their relatedness to study drug or procedure to the DCC within 24 hours of awareness or initial assessment. The DCC will then notify the sIRB and NIDDK. These reporting will follow the criteria outlined in 21 CFR 312.32(c). The SAC will be blinded to the randomization code and will determine if the event is unexpected and define the relationship to NR based on section 8.3.3.2. An adverse event is considered "unexpected" if it is not listed in the study protocol (21 CFR 312.32(a)). If a determination is made that a serious adverse event which is not exempt and has a reasonable possibility of having been caused by a study procedure or the study drug, it will be classified as a suspected adverse reaction. If the suspected adverse reaction is unexpected, it will be classified as a SUSAR.

The DCC will report all unexpected deaths, serious and treatment related adverse events, and SUSARs to the DSMB and NIDDK within 7 working days after receipt of the report from a

clinical site. A written report will be sent to the DSMB, FDA, local IRB, and the sIRB within 15 calendar days. The DSMB will also review all reported adverse events and clinical outcomes during scheduled DSMB meetings. The DCC will distribute the written summary of the DSMB's periodic review of reported adverse events to the local IRB and sIRB in accordance with NIH guidelines (*http://grants.nih.gov/grants/guide/notice-files/not99-107.html*).

In addition, (1) serious, unexpected suspected adverse reactions, (2) findings from other clinical, animal, or in-vitro studies that suggest significant human risk, and (3) a clinically important increase in the rate of a serious suspected adverse reaction will be reported to all investigators, sIRB, local IRB, the FDA, and the DSMB no later than 15 calendar days after determining that the information qualifies for reporting [21 CFR 312.32(c)(1)].

Clinical Outcomes that will be Exempt from Serious Adverse Event Reporting

Pre-specified laboratory safety endpoints will be designated to evaluate possible laboratory abnormalities that might be seen with NR based on previous studies with NR (i.e., <10% reduction in hemoglobin and >25% reduction in platelet counts from baseline).

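### The haemoglobin safety endpoint in section 8.3.6 is a fall smaller than 10%, opposite in direction to the platelet endpoint beside it, so read literally it counts small falls and omits larger ones.

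*Combined protocol and SAP*

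**What the plan says.** Section 8.3.6 states: "Pre-specified laboratory safety endpoints will be designated to evaluate possible laboratory abnormalities that might be seen with NR based on previous studies with NR". The bracket that follows gives the definitions: "<10% reduction in hemoglobin and >25% reduction in platelet counts from baseline". Both stand under the heading "Clinical Outcomes that will be Exempt from Serious Adverse Event Reporting".

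The same 10% figure appears in section 2.3.1, in the list of rare risks, where it covers both cell lines: "Hematologic profile e.g., <10% reduction in hemoglobin and platelet counts". There it describes the size of an effect that NR may have, not an event to be counted.

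Haemoglobin appears in no other endpoint definition. The primary safety endpoint (section 3) uses serious events of grade 3 or higher and platelets. The laboratory results flagged as expected events in section 8.3.4 are platelets, liver tests and CPK. Section 9 names no haemoglobin analysis.

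The data come from Table 4 in section 8.2, which lists "Daily CBC and platelets" for Days 1 to 10. Section 8.2 also limits collection: "The safety clinical laboratory parameters will be performed at each visit while hospitalized".

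**The concern.** An adverse laboratory endpoint should be met by changes larger than a limit. The platelet criterion does this. The haemoglobin criterion, in the same bracket, is met by changes smaller than its limit and is not met by larger ones.

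Section 2.3.1 gives a reason to watch haemoglobin. It reports a mean fall of 0.4 g/dL (p = 0.04) in an open-label dose-escalation study of 8 healthy subjects. If NR lowers haemoglobin by more than 10% in some participants, this endpoint will not show it. Those participants may count as events only because they also had a smaller fall on another day, or they may not count at all. Section 8.3.6 holds the protocol's only percentage-change criterion for haemoglobin, so no second definition corrects it.

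**Working it through.** The plan states no rate, power or sample size for this endpoint, so there is no figure of its own to reproduce.

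**Direction.** Take a baseline of 12.0 g/dL, chosen for illustration.
- A fall to 11.6 g/dL is 0.4/12.0 = 3.3%, which is under 10%, so it counts.
- A fall to 8.5 g/dL is 3.5/12.0 = 29%, which is not under 10%, so it does not count.

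**Inputs for the no-effect rate.**
- Number of values: daily counts on Days 1 to 10 give one baseline and up to k = 9 later values. Early discharge gives fewer, and k = 4 is assumed as an example.
- Counting rule: at least one occurrence, as section 9.4.2 uses for events. Section 9 does not name this criterion, so applying the rule to it is an assumption.
- SD of the percentage change: not given for this population, and assumed to be 3.3% to 15%. The lower end comes from the 8-subject study. A paired t-test with 7 degrees of freedom and p = 0.04 has t = 2.52, so SD = 0.4 × √8 / 2.52 = 0.45 g/dL. That is 3.2% of a baseline of 14 g/dL and 4.5% of a baseline of 10 g/dL.
- Correlation between changes on different days: not given. A value of 0.5 corresponds to independent days that share one baseline; 0.8 is assumed for days that are themselves correlated.

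**Exact case.** If the baseline and k later values are independent with the same distribution, the baseline is the lowest of the k + 1 values with probability 1/(k + 1). So P(at least one later value below baseline) = k/(k + 1). For k = 9 this is 9/10 = 90%, and for k = 4 it is 4/5 = 80%. The result does not depend on the SD, so varying the SD alone is not a sensitivity check on it. The SD enters only through falls of 10% or more.

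**Simulation.** The model is a normal percentage change with mean zero and 400,000 draws per case. The table gives the share with at least one fall above 0 and below 10%.

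| SD of change | k = 9, corr. 0.5 | k = 9, corr. 0.8 | k = 4, corr. 0.5 | k = 4, corr. 0.8 |
|---|---|---|---|---|
| 3.3% | 90% | 76% | 80% | 69% |
| 7.8% | 90% | 74% | 78% | 65% |
| 15% | 84% | 68% | 64% | 55% |

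Other counting rules give lower shares. At a single time point the share is Φ(0) − Φ(−10/SD), which is 50%, 40% and 25% at the three SDs. Classified by the lowest of nine values (correlation 0.5), it is 89%, 52% and 22%.

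**Response to harm.** Now assume a sustained mean fall of 15% with NR, nine values and correlation 0.5. The at-least-once share drops from about 90% to 28% at SD 3.3%, 52% at SD 5% and about 68% at SD 7.8%. In that scenario the arm with the larger falls has fewer events.

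**Direction reversed.** For illustration, count a fall of 10% or more at least once, with no effect. The share is 0.3% to 1% at SD 3.3%, 19% to 39% at SD 7.8% and 41% to 68% at SD 15%, over the same values of k and correlation.

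**The case against.** The strongest defence is that the bracket stands under a heading about exemptions. On that view, a fall under 10% is the size of change expected with NR and exempted from serious adverse event reporting, and larger falls lie outside the exemption. The match with section 2.3.1 supports this. It does not rescue the text. The sentence calls these items endpoints, and a fall under 10% would hardly ever be a serious adverse event, so exempting it achieves little. The platelet figure beside it cannot be an expected upper size either, because section 2.3.1 gives under 10% for platelets too. Section 8.3.6 then lists anaemia as exempt from adverse event reporting unless judged related or of uncertain relationship, so the status of larger falls stays unclear.

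Other parts of the defence stand. A reader might infer that the trial is blind to large haemoglobin falls. The documents do not support that. Section 8.3.1 captures all grade 3 and 4 events. Section 8.3.4 records abnormal laboratory results, haematology included, when the investigator judges them clinically important. Section 8.3.5 reports results that become abnormal during the study. Section 8.3.6 has outcomes such as anaemia collected in both arms, and its exemption concerns reporting, not collection.

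A reader might also infer that the main safety comparison is compromised. It is not: neither the primary safety test in section 9.4.2 nor the interim rule in section 9.4.6 uses haemoglobin.

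The prior evidence for a haemoglobin effect is also mixed. Section 2.3.1 calls the 0.4 g/dL fall slight. It reports no significant haemoglobin difference from placebo in AKI patients given NR with pterostilbene, no haematological changes in a 12-person crossover study, and similar haematology across arms in the 140-person trial.

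**Conclusion.** The concern holds for this one definition. Its direction is wrong for a safety endpoint; this follows from the text and needs no assumption about variability. Read literally as an endpoint, it cannot show a larger fall with NR.

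The no-effect share of about 55% to 90% rests on the assumed SD, correlation and number of values, and on an at-least-once count. A reader might take 90% as the rate to expect. It is only the case of nine complete, independent post-baseline values, and participants discharged early will not have nine. A single time point or the lowest value gives less.

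The defect affects one laboratory safety summary and the wording of an exemption. How the mismatch arose cannot be established from the documents; the repeat of the section 2.3.1 wording only suggests a source. Section 2.3.1 describes a risk and sets no event limit, so reading 10% as the intended limit would be an inference.

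**What to change.** In section 8.3.6, restate the haemoglobin endpoint as a fall from baseline larger than a limit, in the same direction as the platelet criterion. The upper edge of the range in section 2.3.1 is a natural candidate for the sponsor to confirm. Before confirming it, the sponsor should look at the SD of haemoglobin change in this population, because the no-effect rate of a 10% rule runs from 0.3% to 68% over the assumptions above.

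Place the definition outside the heading on exemption from serious adverse event reporting. Otherwise, correcting the direction would appear to exempt the large falls. Reconcile the wording with the risk list in section 2.3.1, the flagged results in section 8.3.4 and the anaemia entry in section 8.3.6.

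Report the endpoint by arm from the blood counts collected. State the number of values per participant, because daily values exist only while participants are in hospital.

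The cost is one line of protocol wording and one row in the safety tables. No new sampling is needed.
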